5.1.3.3. Intensive Subject Glycemic Surveillance and Management

In this treat-to-target study, which includes the discontinuation of prandial insulin in subjects randomly allocated to the albiglutide plus insulin glargine treatment arm as well as the intensification of basal-bolus insulin in subjects randomly allocated to the insulin glargine plus insulin lispro treatment arm, it is important that subjects receive adequate diabetic patient education and training and detailed clear explanations regarding all required study procedures related to glycemic management (see Section 6.2.4 and Section 6.2.5). It is also imperative that study investigators closely monitor available subject information and apply prompt medical judgment as necessary to maintain appropriate glycemic control.

To facilitate subject surveillance by the study investigator, the investigator will have access to information collected in the subject's e-diary, such as daily SMBG

measurements (see Section 6.2.2), daily insulin use (see Section 6.2.5), and subject-reported hypoglycemia (see Section 6.3.1). In addition, study investigators will receive notification of extreme SMBG measurements (i.e., SMBG measurements ≤ 50 mg/dL [≤ 2.8 mmol/L] and SMBG between 50 to 60 mg/dL [2.8 to 3.3 mmol/L]), as well as episodes of severe hypoglycemia recorded in the subject's e-diary. Additional details on these tools are provided in the accompanying SPM.

5.1.3.4. Documentation of Insulin Titration

Surveillance of insulin titration and documentation will be performed centrally. Within approximately 3 business days after a subject's study visit/telephone contact, the investigator must ensure that the following data are available for review by GSK/PPD:

[figure not shown]
- Subject's SMBG values from the last 3 available days (at least 2 of which are consecutive) in the week before the study visit/telephone contact
- Insulin doses for 3 days (at least 2 of which are consecutive) in the week before the next study visit/telephone contact
- Insulin doses recommended until the next study visit/telephone contact
- Comments on any deviation to the insulin titration algorithms must be entered into the eCRFs

The data regarding titration deviations will be reviewed by GSK/PPD. Based on this information, an inquiry as to why the investigator chose to deviate from the titration algorithm may be made, particularly when details of any SMBG readings, time, and date, or hypoglycemic symptoms used in such a decision are not provided or lack clarity. Not all deviations will lead to inquiry. When the investigator receives an inquiry, a response with the reasons for not adhering to the titration guideline should be sent to GSK/PPD within approximately 3 days. Depending on the response, additional inquiries may be sent.

5.1.3.5. Re-introduction of Insulin Lispro in the Albiglutide Treatment Group

Basal insulin plus once-weekly albiglutide may not provide adequate control of postprandial hyperglycemia in some subjects previously treated with basal-bolus insulin therapy. For subjects randomly assigned to treatment with albiglutide who continue to experience significant postprandial glucose excursions (i.e., >180 mg/dL [>10.0 mmol/L]), insulin lispro may be re-introduced after Week 8 (i.e., 4 weeks after discontinuation of insulin lispro and uptitration to albiglutide 50 mg). Re-introduction of insulin lispro will follow the standardized, stepwise approach as shown in [Figure 2](#).

Following the re-introduction of insulin lispro, subjects will remain in the study and continue to take insulin lispro in addition to randomly assigned once-weekly albiglutide and background insulin glargine. As determined by the investigator, subjects requiring re-introduction of insulin lispro may be seen more frequently by arranging unscheduled visits until their glycemic control has stabilized.

Figure 2 Re-introduction Algorithm for Insulin Lispro

HbA_{1c} = glycosylated hemoglobin. SMBG = self-monitored blood glucose.

Note: Figure modified with permissions (pending) from [Abrahamson 2012].

1. Post-breakfast (Prior to Lunch), post-lunch (Prior to Dinner), or post-dinner (i.e., Prior to Bedtime).
2. Mean of measurements from the last 3 available days (at least 2 of which are consecutive) in week before the next study visit/telephone contact. If measurements from 3 days (at least 2 of which are consecutive) are not available, the dose adjustment should be delayed until the next scheduled study visit/telephone contact; unless in the investigator's judgment, a dose adjustment is warranted. The subject should be retrained on the importance of SMBG measurements.
3. For insulin lispro dose titration, see Section 5.1.3.2, Table 4.

The algorithm in Figure 2 for re-introduction of insulin lispro should apply in the majority of circumstances; however, as the intent of glycemia management in subjects with T2DM is to individualize treatment goals to achieve a target HbA_{1c} level as close to normal as possible without significant hypoglycemia or other adverse effects of treatment, the investigator should use his/her judgment in determining benefit:risk of further insulin dose adjustment and modification, accordingly. In the event a subject experiences significant evidence of hyperglycemia (e.g., symptoms of polyuria and polydipsia and laboratory evidence of hyperglycemia) and the investigator determines that further dose adjustment with insulin is not in the best interest of the subject and that the subject requires rescue with another antidiabetic medication, the subject should be discontinued from the study and the appropriate rescue therapy initiated. Additionally, subjects not achieving a predefined threshold for glycemic control (confirmed persistent FPG \geq 270 mg/dL [15.0 mmol/L]) at least 8 weeks after randomization may be considered

for study withdrawal based on the discretion of the investigator and the medical monitor (see Withdrawal Criteria in Section 4.5).

5.2. Treatment Assignment

Randomized treatment assignment will be done via the interactive voice response system (IVRS), and randomization will be implemented based on a sequestered fixed randomization schedule. Site personnel will call the IVRS to execute each randomization and initiate shipment of the investigational product once a subject has met all prerequisites for randomization and has completed all scheduled screening and standardization procedures.

Subjects will be assigned to study treatment in accordance with the randomization schedule. Eligible subjects will be stratified by screening HbA_{1c} value (<8.0% versus ≥8.0%), age (<65 years versus ≥65 years), and current use of background metformin (metformin use versus no metformin use).

Approximately 794 subjects will be randomly assigned to 1 of the following 2 open-label treatment groups in a 1:1 ratio such that

- Approximately 397 subjects are randomly assigned to albiglutide + insulin glargine (with or without metformin)
- Approximately 397 subjects are randomly assigned to intensification of insulin glargine + insulin lispro (with or without metformin)

Site personnel will receive a randomization notification indicating the unique subject identifier, the treatment assignment, and the date and time of randomization. Each subject number will be a unique identifier. Once a subject number has been assigned, the number will not be reused even if the subject withdraws before receiving any randomized study medication.

5.3. Blinding

This will be an open-label study. An open-label study design was selected because insulin lispro is an injectable medication and thus double-blinding the study would require multiple dummy injections, which may not be in the best interest of the subject. Additionally, because insulin lispro will only be discontinued in the albiglutide treatment group, it is not feasible to blind the study. Furthermore, use of an objective laboratory endpoint will help mitigate bias that might otherwise be introduced if an open-label study design was not adopted.

5.4. Product Accountability

In accordance with local regulatory requirements, the investigator, designated site staff, or head of the medical institution (where applicable) must document the amount of investigational product dispensed and/or administered to study subjects, the amount returned by study subjects, and the amount received from and returned to GSK, when

applicable. Product accountability records must be maintained throughout the course of the study.

5.5. Treatment Compliance

Accountability will be done for the investigational product (albiglutide) and other study treatments (insulin glargine and insulin lispro) at the time points specified in the Time and Events Table ([Table 5](#)). Subjects will be instructed to return all unused investigational product and used injector pens in order to perform drug accountability and determine compliance.

Acceptable overall compliance for IP (albiglutide) and other study treatments (insulin glargine and insulin lispro) in this study will be $\geq 80\%$. Site personnel should confirm that subjects are taking their doses of albiglutide and insulin glargine and lispro insulin, if appropriate, as prescribed by their physician. Adherence will be monitored for the duration of the study.

Subjects will be instructed to take their metformin as prescribed by their physician and will continue on this dose for the duration of their participation in the study unless there is a decline in kidney function (Section [5.1.1](#) and [Table 2](#)). Adherence to dosing instructions for metformin will be monitored for the duration of the study.

5.6. Concomitant Medications and Nondrug Therapies

All medications taken at any time from 3 months prior to Screening to the Follow-up visit will be recorded in the eCRF. The minimum requirement is that drug name and the dates of administration are to be recorded.

5.6.1. Permitted Medications and Nondrug Therapies

Note: Albiglutide causes a delay of gastric emptying and thereby has the potential to impact the absorption of concomitantly administered oral medications. During the albiglutide development program, drug interaction studies were conducted with digoxin, warfarin, oral contraceptives, and simvastatin, which demonstrated no clinically relevant pharmacokinetic (PK) or pharmacodynamic effects. Investigators should use clinical judgment and caution when prescribing concomitant medications.

The following concomitant medications are permitted:

- As-needed use of prescription and over-the-counter medications at the discretion of the investigator

Although stable doses of all concomitant medications are preferable, changes in medications during the study to appropriately treat clinical conditions that might arise, including worsening blood pressure control and dyslipidemia, are allowed.

Subjects will be monitored for renal function (eGFR calculated using the MDRD formula) during the study. Metformin and concomitant medications should always be

used within the label recommendations and stopped or adjusted according to the status of renal function and clinical conditions of the subject.

Investigators must adhere to the local labeling of the respective country (e.g., the summary of product characteristics in relevant European countries or the FDA-approved prescribing information) for all nonexcluded medications.

5.6.2. Prohibited Medications and Nondrug Therapies

Subjects must not use any of the following medications:

- Any antidiabetic medications (e.g., GLP-1R agonist, dipeptidyl peptidase-IV inhibitor, SU, thiazolidinedione, meglitinide, sodium-glucose transporter 2 inhibitor, or commercially available premixed basal and prandial insulin) other than the treatment they have been randomly assigned to, insulin glargine, insulin lispro, and their current regimen of background metformin, if applicable, being taken at Screening.
- Oral or systemically injected corticosteroids (inhaled, intra-articular, epidural, and topical corticosteroids are allowed); short courses of oral steroids (single dose or multiple doses for up to 7 days) may be permitted provided these cases are discussed with the medical monitor
- Antiretroviral drugs
- Prescription and over-the-counter weight loss drugs

If a subject receives a prohibited medication, a protocol deviation will be reported and continuation in the study will be discussed with and agreed upon by the medical monitor.

5.7. Treatment Between Week 26 (End of Treatment)/Early Withdrawal and After the Follow-up Visit

5.7.1. Treatment Between Week 26 (End of Treatment)/Early Withdrawal and Follow-up

After completion of the end-of-treatment (Week 26) or early withdrawal visits, subjects will return to the study center in 4 weeks for the Follow-up visit. During this time, subjects will continue insulin glargine or insulin glargine plus insulin lispro to maintain adequate glycemic control.

For subjects in the albiglutide plus insulin glargine treatment arm, the last dose of once-weekly albiglutide will occur at Week 25. As needed, insulin lispro may also be re-introduced during this period according to the re-introduction of insulin lispro algorithm provided in Section 5.1.3.5. Insulin glargine alone (in subjects for whom insulin lispro has not been re-introduced) or insulin glargine and insulin lispro (in subjects for whom insulin lispro has been re-introduced) can be adjusted to achieve or maintain glycemic targets as close to normal as possible without untoward hypoglycemia

in accordance with product labeling in the respective country and standards of care at the study center.

For subjects in the insulin glargine plus insulin lispro treatment arm, both insulin glargine and insulin lispro may be adjusted to achieve or maintain glycemic targets as close to normal as possible without untoward hypoglycemia in accordance with product labeling in the respective country and standards of care at the study center.

Note: During this time, subjects must not use any prohibited medications or nondrug therapies (see Section [5.6.2](#)).

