4.5. Withdrawal Criteria

Every effort should be made to keep subjects in the study. The reasons for subjects not completing the study will be recorded.

The following **will** require withdrawal from the study:

- AE, which, in the opinion of the investigator precludes effective participation of the subject or poses a safety concern
- Elevation of liver function test results meeting any of the liver stopping criteria (see Section 6.3.6)
- Severe allergic/hypersensitivity reaction that is considered by the investigator to be attributable to randomized study medication or without a likely alternative etiology (see Section 6.3.9.3)
- Confirmed acute or chronic pancreatitis (see Section 6.3.9.4)
- Confirmed medullary thyroid cancer (see Section 6.3.9.6)
- Recurrent severe hypoglycemia or recurrent nocturnal hypoglycemia during the Treatment Period posing a potential risk to the subject, as judged by the investigator
- Pregnancy or intention of becoming pregnant
- Major protocol deviation if withdrawal from the study is mandated by the medical monitor (the investigator should discuss the protocol deviation with the medical monitor before withdrawing study medication)
- GSK-defined Sentinel Event. The medical monitor will advise the investigator if an SAE meets the criteria of a true Sentinel Event (e.g., without a clear alternate etiology) for which withdrawal is required (see Section 6.3.7.3)

In addition, a subject may be withdrawn from the study for the following reasons:

- FPG >270 mg/dL (15.0 mmol/L) at least 8 weeks after randomization on 3 consecutive days (by blood glucose meter), which is confirmed by a central laboratory (to be done within 2 weeks of the home glucose monitoring). Continuation of the subject will be at the discretion of the investigator after consultation with the medical monitor
- Lost to follow-up
- Study closed/terminated or investigator site closed (where subject transfer to another site is not possible)
- Subject decision (reason to be documented in the electronic case report form [eCRF], if specified by the subject)
- Investigator discretion

Note: Use of a prohibited medication constitutes a protocol deviation. Continuation of the subject in the study will be discussed with the medical monitor, and the decision of continuation or withdrawal will be documented.

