Should a subject fail to attend the clinic for a required study visit, the site should attempt to contact the subject and reschedule the missed visit as soon as possible. The site should also counsel the subject on the importance of maintaining the assigned visit schedule and ascertain whether or not the subject wishes to and/or should continue in the study based on previous noncompliance. In cases where the subject does not return for the

rescheduled visit or cannot be reached to reschedule the missed visit, the site should make every effort to regain contact with the subject (3 telephone calls and if necessary a certified letter to the subject's last known mailing address) so that they can appropriately be withdrawn from the study. These contact attempts should be documented in the subject's medical record. Should the subject continue to be unreachable, then and only then will he/she be considered to have withdrawn from the study with a primary reason of "Lost to Follow-up." For all other subjects withdrawing from the study, an alternative reason for discontinuation should be recorded in the eCRF.

The half-life of albiglutide is approximately 5 days, and significant therapeutic concentrations can persist for 3 to 4 weeks after discontinuation. Therefore, the investigator should use caution when prescribing treatment after the withdrawal of active study medication, taking into consideration the long half-life of albiglutide. Thereafter, postwithdrawal treatments may be modified over time, as needed, at the investigator's discretion.

Study medication withdrawal will require withdrawal from the study. Withdrawn subjects will not be replaced.

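### The Note in Protocol Section 5.7.1 bans, without exception, the rescue drug that Section 5.1.3.5 tells the site to start in an albiglutide-arm subject discontinued for that reason

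*Protocol*

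**What the plan says.** Section 5.1.3.5, headed for the albiglutide group, deals with a subject who has significant evidence of hyperglycemia. The rule applies if "the investigator determines that further dose adjustment with insulin is not in the best interest of the subject" and a different drug is needed. The instruction is then: "the subject requires rescue with another antidiabetic medication, the subject should be discontinued from the study and the appropriate rescue therapy initiated".

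Section 4.5.1 has discontinued subjects complete the early withdrawal assessments and come back 4 weeks later. Section 5.7.1 covers that interval and names early withdrawal, alongside Week 26, as one of its two starting points. For glycemic control it says that "subjects will continue insulin glargine or insulin glargine plus insulin lispro to maintain adequate glycemic control". Its closing Note reads "During this time, subjects must not use any prohibited medications or nondrug therapies" and refers to Section 5.6.2.

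Section 5.6.2 bans any antidiabetic "other than the treatment they have been randomly assigned to, insulin glargine, insulin lispro, and their current regimen of background metformin". Use of a prohibited drug is a reportable deviation, after which "continuation in the study will be discussed with and agreed upon by the medical monitor".

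**The concern.** Section 5.1.3.5 takes effect only once the investigator has judged that more insulin is the wrong answer and that a different drug is needed. Section 5.7.1 then leaves that subject with insulin alone, apart from any background metformin, until Follow-up. A site that follows the Note literally would withhold or delay a rescue that the protocol itself directs, in a subject who may be symptomatic. A site that follows Section 5.1.3.5 could find its action logged as a deviation. What is at stake is the care of a few withdrawn subjects and clean deviation reporting.

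**Working it through.** No arithmetic decides this point. It rests on setting the current sections side by side for one subject.

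| Step | Protocol section | What it requires |
|---|---|---|
| 1 | 5.1.3.5 | Albiglutide arm, more insulin not appropriate, another antidiabetic needed: discontinue and start rescue |
| 2 | 4.5.1 | Complete early withdrawal assessments, return 4 weeks later |
| 3 | 5.7.1, text | In those 4 weeks: glargine, or glargine plus lispro |
| 4 | 5.7.1, Note | In those 4 weeks: nothing prohibited by 5.6.2 |
| 5 | 5.6.2 | Prohibited: every antidiabetic except randomized treatment, glargine, lispro and background metformin |

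The rescue drug in step 1 is by its terms something other than more insulin, so it falls under the ban in step 5. Step 4 carries that ban into the interval in which step 1 would start the drug. Neither 5.6.2 nor the Note contains a rescue exception. The interval is 4 weeks × 7 = 28 days per affected subject.

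Four places might resolve the conflict, and none does:

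- **Section 4.5** says "the investigator should use caution when prescribing treatment after the withdrawal of active study medication", because of albiglutide's long half-life, and then leaves later modification to the investigator. It assumes that some prescribing will follow withdrawal, but does not mention or lift the 5.6.2 ban.
- **Section 5.7.2** repeats that language, but under a heading about treatment after the Follow-up visit.
- **Section 5.6.2** gives the medical monitor a say over whether a subject stays in the study once a deviation has occurred. That is not permission to use the drug, and means little for someone already discontinued.
- **Section 3.1** excepts immediate safety concerns from its rule against waivers. That may cover an urgent case, but a treatment the protocol directs should not depend on a waiver.

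**Analyses.** The visit schedule has HbA1c at the early withdrawal visit and none at Follow-up. SAP Section 11.3.3 accepts an early withdrawal result for efficacy if it falls within 14 days of last dose. Rescue begun after those assessments therefore cannot alter an HbA1c value that the primary model uses. SAP Section 11.1.1 requires completed Week 26 treatment for the Per-Protocol Population, so a subject withdrawn before then is already outside it.

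**The case against.** The best defense is that a specific instruction governs a general reminder. Section 5.1.3.5 says exactly what to do, while the Note merely points back to 5.6.2. The deviation sentence in 5.6.2 concerns continuation in the study, which is moot after discontinuation, and the examples in 5.1.3.5 (polyuria, polydipsia, laboratory evidence) come close to the safety exception in Section 3.1. Many investigators would read it this way and start rescue. This weakens any claim that rescue would in practice be refused, and it makes a logged deviation possible rather than certain. It does not remove the conflict: the documents state no order of precedence, and the Note is itself specific to this interval and expressly reaches early withdrawals.

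A reader might also infer a wider problem covering every subject, in either arm, withdrawn under the criterion "FPG >270 mg/dL (15.0 mmol/L) at least 8 weeks after randomization on 3 consecutive days". The documents do not support that. Section 4.5 directs no other antidiabetic for those subjects. Section 5.7.1 allows glargine and lispro to be adjusted in the control arm, and allows glargine adjustment and lispro re-introduction in the albiglutide arm, so they can be treated within the Note. The investigator discretion in Section 4.5 follows sentences about albiglutide persisting for 3 to 4 weeks. It can be read as starting after that period, which would agree with a 4-week restriction, and it is weak authority for the lispro arm.

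One further caution stands. Section 5.1.3.5 does not say whether rescue comes before or after the early withdrawal HbA1c sample. Section 4.5.1 asks for those assessments immediately on discontinuation, so overlap is unlikely, but the text does not exclude it.

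**Conclusion.** The contradiction is real and narrow: Section 5.1.3.5 against the Section 5.7.1 Note, for albiglutide-arm subjects discontinued because they need another antidiabetic. It is a rule that gives the wrong result when followed as written, rather than a missing detail.

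Severity is minor. The number affected cannot be computed because the documents give no rescue rate; Protocol Section 8.3.5.1.3 does not expect substantial withdrawal for lack of efficacy. Sample size, type I error and power are untouched. That no effect on the primary analysis is expected rests on one assumption: rescue starts after the early withdrawal HbA1c sample.

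**What to change.** Add to the Note in Section 5.7.1: *except rescue antidiabetic therapy initiated under Section 5.1.3.5 in a subject discontinued for that reason, which may start after the early withdrawal assessments (or at once if clinically urgent), with caution for albiglutide's half-life, and is not a protocol deviation.*

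The exception should stay this narrow. Lifting the ban for all early withdrawals would admit non-study antidiabetics where nothing in the protocol calls for them.

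The cost is one clause in the next amendment and a short memo to sites, with no new visits, procedures or data fields. There is a small downside. SAP Section 5.5 and Appendix 4 count albiglutide-arm adverse events, including hypoglycemia, as on-therapy until 25 days after last dose, so events after rescue starts can fall in that window. They can be recognized, because Protocol Section 5.6 has medications recorded up to the Follow-up visit.
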